7. INFORMED CONSENT PROCESS

*Specific description of informed consent process: Informed consent will be obtained from all participating subjects prior to enrollment in the study. (See attached informed consent form) The risks, benefits and alternatives will be discussed with potential subjects by clinic investigators listed above (Drs. [name], [name] and [name]) at time of appointment at Loma Linda Sinus and Allergy center. Patient information will be kept private and there will be time for decision-making/discussion prior to enrollment in the study. Patient who are able to verbalize/demonstrate their understanding and are able to give informed consent will be considered. Subjects will be identified by state ID or Driver's license and will be randomized into one of two study groups by flip of a coin.*

*Coding system: diagnosis and office visits will be coded in the standard fashion.*

*Privacy of Medical and Research Records information/medical records: Patient information and study data will be kept as hard copy by PI in locked desk/room and some study data will be kept on encrypted/protected flash drive by PI.*

*Medical Release forms, HIPAA compliance/authorization form: See attached form*

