**6. SUBJECT RECRUITMENT & SCREENING**

*Number of Subjects: ~40*

*Subject Age Range: ≥18 years of age, ≤80 years of age*

*Subject Gender: Both*

*Racial/Ethnic Distribution: Any*

*Target Study Population: Patients without nasal polyps who suffer from chronic rhinosinusitis.*

*English/Non-English Speaking Subject Info: Translators will be provided for non-English speaking patients*

*Certified Translated Consent Form Use: None*

*Recruitment Material Type Info: All patients who present to Loma Linda Sinus and Allergy center meeting inclusion criteria will be asked to participate*

*Vulnerable Subject Info: N/A*

*Recruitment Method Info: Patients without nasal polyps as documented by endoscopy and who are not currently taking antibiotics or nasal/oral corticosteroids will be prospectively recruited. This will be a randomized blinded study. Patients will be randomized into three groups- Group 1 will received oral antibiotics (Bactrim or Augmentin) nasal steroid sprays (fluticasone) along with nasal saline irrigation , Group 2 will receive oral antibiotics, steroid nasal spray and in addition oral steroids (prednisone) at a tapered dosage for 6 days, and Group 3 will receive oral antibiotics, steroid nasal spray and in addition oral steroids at a tapered dosage for 20 days. The investigator will be blinded as to which group the subjects are placed.*

*Description of consent precautions regarding subject rights and welfare: Informed consent will be obtained from all patients after they have been given the opportunity to have their questions answered.*

*Pregnancy Status Info: Pregnant patients will not be included in study*

3

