## **8. STUDY DESIGN**

*a. Background or rationale for this study: Chronic sinus infections (chronic sinusitis or CRS) are common conditions that affect millions of Americans. This disease can be divided into two main patient groups: Patients with chronic rhinosinusitis without nasal polyps (CRSsNP) and those with nasal polyps (CRSwNP). We will be focusing on the non-polyp group. While this is a common disorder, medical treatments for this condition vary considerably and little is known how and why different treatments work in some individuals and not in others. Topical nasal steroids and oral antibiotics are the mainstay and standard of care for both CRSsNP and CRSwNP. Oral steroids are commonly given for both of these sinusitis variants, however their role in non-polyp CRS patients is less well delineated. The purpose of this research study is to better*

*understand whether orally administered steroids results in superior results when compared with nasally sprayed steroids in this population. The investigators will compare patients with chronic sinusitis who are treated with antibiotics, topical nasal sprayed steroid therapy, and compare them to chronic sinusitis patients who receive antibiotics and nasally sprayed steroid therapy along with a short course or long course of oral steroids. The goal is to determine if oral steroids have a role in CRSsNP, and if so, the most effective dosage.*

*b. Objectives. To compare the effectiveness of topical nasal steroid sprays, oral antibiotics and saline nasal irrigations versus topical nasal steroids, oral antibiotics, saline nasal irrigation + oral corticosteroids (prednisone) in CRS patients without nasal polyps.*

*c. Procedures involved (Research Interventions). Chronological order of all research interventions, distinguishing standard of care vs. research intervention:*

*4*

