*1. At the time of enrollment nasal endoscopy will be performed to confirm that the patient does not have evidence of nasal polyps. Office-based sinus CT scan will also be completed on initial visit. Lund-McKay score at initiation of treatment will be one a determinate of study eligibility. (Lund-McKay staging system is currently the most widely accepted system to radiographically characterize and diagnose CRS. A score of 6 or greater indicates significant sinus disease and meets inclusion criteria for study. See below table 1 for Lund-McKay staging system.) Note: Endoscopy and CT of paranasal sinuses are the standard of care for evaluation of patients with symptoms of CRS and will be offered to all patients presenting with these symptoms regardless of study enrollment status.*

*2. Subjects will be asked to fill out a SNOT 22 survey before the start of therapy.*

*(SNOT 20 form attached).*

*3. Nasal endoscopy score will also be obtained during initial visit. (Nasal endoscopy scoring form attached). This exam is part of the standard of care.*

*4. Subjects will be randomized into 3 groups via an electronic random generator (see below)*

*1. Group 1: Treated with oral antibiotics, nasal steroid spray and saline rinses for 3 weeks (standard of care)*

*2. Group 2: Treated with above + Prednisone 6 day tapered dosage (standard of care)*

*3. Group 3: Group 2: Treated with above + Prednisone 20 day tapered dosage (standard of care)*

*4. Random generator:*

*5*

*5. Patients will return to office at 4 weeks (following 3 weeks of oral antibiotics, nasal steroid spray, nasal saline irrigation + prednisone for patients in Groups 2 and 3), At that time, patients will be asked to fill out SNOT 22 survey, nasal endoscopy and CT scan to assess response to treatment. (standard of care).*

*6. At the 4 week follow up, patients will be asked to fill out SNOT 22 survey, and undergo nasal endoscopy. (standard of care).*

*d. Alternative procedures, if any, that are not included in the study but might be advantageous to the subject - None*

*e. If any deception is required for validity of this study, explain why this is necessary and how subject(s) will be debriefed. - None*

*f. Concise review of literature that supports the rationale, objectives, and methodology of the proposed study.*

*1. Chronic sinus infections (chronic sinusitis or CRS) are common conditions that affect millions of Americans. This disease can be divided*

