3. Prednisone 6 day taper given as 30mg PO QD for 2 days, 20mg PO QD for 2 days, 10mg PO QD for 2 days, then stop. Common side effects: Fluid retention, increased sweating, headache, insomnia, nervousness, mood swings, edema, muscle weakness, BP elevation, facial erythema, menstrual irregularities, hypokalemia, intraocular pressure increase, shortness of breath, weight gain.

4. Prednisone 20 day taper given as 40mg PO QD for 5 days, 30mg PO QD for 5 days, 20mg PO QD for 5 days, 10mg PO QD for 5 days, then stop. Common side effects: Fluid retention, increased sweating, headache, insomnia, nervousness, mood swings, edema, muscle weakness, BP elevation, facial erythema, menstrual irregularities, hypokalemia, intraocular pressure increase, shortness of breath, weight gain.

5. Nasal saline ad lib

g. If an Investigational Device (ID) is involved, provide the following information: (1) name of device, (2) manufacturer, (3) status with Food and Drug Administration and ID#, (4) review of animal studies and previous human studies, (5) reported adverse effects. – Not applicable

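### Section 7 allocates subjects to two groups by coin toss, while section 6 has three groups and section 8c allocates three groups by electronic generator

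*Protocol*

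**What the plan says.** The protocol describes allocation in three places.

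- Section 7 (informed consent process): subjects "will be randomized into one of two study groups by flip of a coin". It does not say which two groups are meant or who tosses the coin.
- Section 6 (recruitment and screening): "Patients will be randomized into three groups". It then describes each one: no oral steroid, a 6-day prednisone taper and a 20-day prednisone taper, all on top of antibiotics and nasal steroid spray. It names no method of allocation. The same paragraph adds: "The investigator will be blinded as to which group the subjects are placed".
- Section 8c, step 4: "Subjects will be randomized into 3 groups via an electronic random generator", followed by a list of Groups 1 to 3.

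Other parts of section 8 bear on the number of arms. Section 8a compares patients without oral steroids with patients treated "along with a short course or long course of oral steroids", and states: "The goal is to determine if oral steroids have a role in CRSsNP, and if so, the most effective dosage". Section 8c, step 5, refers to "prednisone for patients in Groups 2 and 3". The drug list in section 8h has an entry for each of the two prednisone courses; the longer one begins "Prednisone 20 day taper given as".

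**The concern.** The number of arms and the way patients reach them are the core of a randomised design, and the protocol gives two incompatible versions of both. Anyone who relies on section 7 would apply or describe a different trial from the one in section 8c. Under the section 7 version, the trial could not meet the whole of its stated goal by randomised comparison.

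A secondary risk depends on something the text does not say. If an enrolling investigator tosses the coin at the consent visit, the toss reveals the assignment, can be repeated and leaves no record. That could conflict with the investigator blinding stated in section 6.

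**Working it through.** The protocol states no per-group sample size, power or allocation ratio, so there is no figure to reproduce. The check compares the texts and then counts what a two-group rule would leave.

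**Step 1. The texts side by side**

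| Place | Groups | Method |
|---|---|---|
| Section 6 | 3, each described | none named |
| Section 7 | 2, not described | coin toss |
| Section 8a | no oral steroid, short course, long course | none named |
| Section 8c, step 4 | 3, each listed | electronic generator |
| Section 8c, step 5 | prednisone in two separate groups | none named |

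The conflict on the number of groups is between section 7 and sections 6, 8a and 8c. The conflict on method is between sections 7 and 8c only. Section 7 is the only place that mentions two study groups or a coin. No amendment log is shown that would mark its sentence as superseded.

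**Step 2. Can the texts be reconciled?** One toss has two outcomes and there are three groups. Section 7 describes no second toss or second stage, so its rule cannot produce the section 8c allocation.

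**Step 3. Expected group sizes.** The input is about 40 subjects (section 6). A fair coin and, for three groups, equal allocation are assumed.

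- Two groups: 40 / 2 = 20 per group.
- Three groups: 40 / 3 = 13.3, about 13 per group.
- Relative difference: (20 − 13.3) / 20 = about one third fewer per group with three groups.

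**Step 4. What each two-group reading leaves.** Three groups give 3 pairwise comparisons (1 v 2, 1 v 3, 2 v 3).

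| Reading of the two groups | Expected numbers, Groups 1/2/3 | Role of oral steroids randomised? | Short v long course randomised? |
|---|---|---|---|
| Groups 1 and 2 | 20/20/0 | yes, short course only | no |
| Groups 1 and 3 | 20/0/20 | yes, long course only | no |
| Groups 2 and 3 | 0/20/20 | no | yes |
| No oral steroid v any oral steroid | about 20 v 20, Groups 2 and 3 combined | yes | no |

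Each of the first three readings keeps 1 of the 3 pairwise comparisons and leaves one regimen without patients. In the fourth, both courses could still be given, but the toss would not decide which. None of the four readings answers both parts of the section 8a goal by randomised comparison.

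**The case against.** The strongest reply is that the sentence in section 7 is leftover wording and that section 8c governs. Section 8c is the ordered procedure and lists the groups at the point of randomisation, whereas section 7 concerns consent and defines no treatments. On that view the splits above are arithmetic on a scenario that the rest of the protocol makes unlikely. That is plausible, and nothing here shows that the trial was run by coin toss. But the protocol has no rule saying which section takes precedence, so a reader cannot tell from it which procedure was approved.

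A second reply is that the title, the objective in section 8b and the benefit statement in section 13 are all framed as with against without oral steroids, which fits two groups. This makes the any-against-none reading at least as natural as the pairings, and under it no regimen need be empty. It does not rescue section 7, because sections 6, 8a, 8c and 8h set out two separate courses and section 8a asks which dosage is best.

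Two narrower points stand. In section 8c the label for the random generator is followed by nothing in the extracted text. A figure or list may have been lost there, so the absence of an allocation ratio is a statement about the visible text only. And the concealment risk rests on an assumption about who tosses the coin; the finding does not depend on it.

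**Conclusion.** The concern holds, with high confidence, and must be fixed. It is a contradiction in the current text about two core design elements: the number of arms (two against three) and the allocation method (coin toss against electronic generator). If section 7 were followed, at least one part of the two-part goal would lose its randomised comparison under every reading. The group sizes, about 20 against about 13, show scale only and rest on about 40 subjects, a fair coin and equal allocation. The contradiction itself rests on no assumption. What is shown is an inconsistent protocol, not a trial run wrongly. Whether the consent form repeats the two-group wording cannot be judged, because it is not at hand.

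**What to change.** Delete the two-group coin-toss wording from section 7 and replace it with a reference to the three-group electronic randomisation in section 8c, so that one number of groups and one method apply throughout. Check the consent form and correct it if it also says two groups.

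As optional good practice, separate from curing the contradiction: generate the allocation list in advance, have it held by an existing team member who does not score outcomes, and reveal each assignment only after consent and baseline scoring.

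The cost is a protocol wording amendment, plus a consent form correction if needed. No patients or procedures are added.

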## **8. STUDY DESIGN**

*a. Background or rationale for this study: Chronic sinus infections (chronic sinusitis or CRS) are common conditions that affect millions of Americans. This disease can be divided into two main patient groups: Patients with chronic rhinosinusitis without nasal polyps (CRSsNP) and those with nasal polyps (CRSwNP). We will be focusing on the non-polyp group. While this is a common disorder, medical treatments for this condition vary considerably and little is known how and why different treatments work in some individuals and not in others. Topical nasal steroids and oral antibiotics are the mainstay and standard of care for both CRSsNP and CRSwNP. Oral steroids are commonly given for both of these sinusitis variants, however their role in non-polyp CRS patients is less well delineated. The purpose of this research study is to better*

*understand whether orally administered steroids results in superior results when compared with nasally sprayed steroids in this population. The investigators will compare patients with chronic sinusitis who are treated with antibiotics, topical nasal sprayed steroid therapy, and compare them to chronic sinusitis patients who receive antibiotics and nasally sprayed steroid therapy along with a short course or long course of oral steroids. The goal is to determine if oral steroids have a role in CRSsNP, and if so, the most effective dosage.*

*b. Objectives. To compare the effectiveness of topical nasal steroid sprays, oral antibiotics and saline nasal irrigations versus topical nasal steroids, oral antibiotics, saline nasal irrigation + oral corticosteroids (prednisone) in CRS patients without nasal polyps.*

*c. Procedures involved (Research Interventions). Chronological order of all research interventions, distinguishing standard of care vs. research intervention:*

*4*

*1. At the time of enrollment nasal endoscopy will be performed to confirm that the patient does not have evidence of nasal polyps. Office-based sinus CT scan will also be completed on initial visit. Lund-McKay score at initiation of treatment will be one a determinate of study eligibility. (Lund-McKay staging system is currently the most widely accepted system to radiographically characterize and diagnose CRS. A score of 6 or greater indicates significant sinus disease and meets inclusion criteria for study. See below table 1 for Lund-McKay staging system.) Note: Endoscopy and CT of paranasal sinuses are the standard of care for evaluation of patients with symptoms of CRS and will be offered to all patients presenting with these symptoms regardless of study enrollment status.*

*2. Subjects will be asked to fill out a SNOT 22 survey before the start of therapy.*

*(SNOT 20 form attached).*

*3. Nasal endoscopy score will also be obtained during initial visit. (Nasal endoscopy scoring form attached). This exam is part of the standard of care.*

*4. Subjects will be randomized into 3 groups via an electronic random generator (see below)*

*1. Group 1: Treated with oral antibiotics, nasal steroid spray and saline rinses for 3 weeks (standard of care)*

*2. Group 2: Treated with above + Prednisone 6 day tapered dosage (standard of care)*

*3. Group 3: Group 2: Treated with above + Prednisone 20 day tapered dosage (standard of care)*

*4. Random generator:*

*5*

*5. Patients will return to office at 4 weeks (following 3 weeks of oral antibiotics, nasal steroid spray, nasal saline irrigation + prednisone for patients in Groups 2 and 3), At that time, patients will be asked to fill out SNOT 22 survey, nasal endoscopy and CT scan to assess response to treatment. (standard of care).*

*6. At the 4 week follow up, patients will be asked to fill out SNOT 22 survey, and undergo nasal endoscopy. (standard of care).*

*d. Alternative procedures, if any, that are not included in the study but might be advantageous to the subject - None*

*e. If any deception is required for validity of this study, explain why this is necessary and how subject(s) will be debriefed. - None*

*f. Concise review of literature that supports the rationale, objectives, and methodology of the proposed study.*

*1. Chronic sinus infections (chronic sinusitis or CRS) are common conditions that affect millions of Americans. This disease can be divided*

*into two main patient groups: Patients with chronic rhinosinusitis without nasal polyps (CRSsNP) and those with nasal polyps (CRSwNP). We will be focusing on the non-polyp group. While this is a common disorder, medical treatments for this condition vary considerably and little is known how and why different treatments work in some individuals and not in others. Topical nasal steroids and oral antibiotics are the mainstay and standard of care for both CRSsNP and CRSwNP. Oral steroids are commonly given for both of these sinusitis variants, however their role in non-polyp CRS patients is less well delineated. The purpose of this research study is to better understand whether orally administered steroids results in superior results when compared with nasally sprayed steroids in this population, and if so, at which dosage. The investigators will compare patients with chronic sinusitis who are treated with antibiotics, topical nasal sprayed steroid therapy, and compare them to chronic sinusitis patients who receive antibiotics and nasally sprayed steroid therapy along with oral steroids. The goal is to determine if oral steroids have a role in CRSsNP. (See below for literature review.)*

6

*g. If an Investigational New Drug (IND) is involved, provide the following information: (1) name of drug, (2) source of drug, (3) dosage and schedule of administration, (4) status with Food and Drug Administration and IND#, (5) review of animal studies and previous human studies, (6) reported side effects.*

– Not applicable to this study

h. For an approved drug used in an experiment, provide similar information:

1. Fluticasone propionate nasal spray 400mcg qday given as 2 sprays (50mcg propionate per spray) to each nostril twice a day daily. Common side effects include: Headache. Back pain, minor nosebleed, menstrual cycle disturbance,

sinus pain, cough, sore throat, sore or white patches inside or around nose

1. Augmentin (amoxicillin/clavulanate 875/125mg) PO BID for 3 weeks.

Common side effects: Diarrhea, nausea, rash, urticarial, pruritis, epigastric discomfort, vomiting, glossitis, stomatitis, candidiasis, LFT elevation

2. If allergic to Augmentin: Bactrim DS

(Trimethoprim/sulfamethoxazole 160/800mg) PO BID for 3 weeks. Common side effects: Nausea/vomiting, rash, diarrhea, dizziness, urticaria, headache, lethargy

3. Prednisone 6 day taper given as 30mg PO QD for 2 days, 20mg PO QD for 2 days, 10mg PO QD for 2 days, then stop. Common side effects: Fluid retention, increased sweating, headache, insomnia, nervousness, mood swings, edema, muscle weakness, BP elevation, facial erythema, menstrual irregularities, hypokalemia, intraocular pressure increase, shortness of breath, weight gain.

4. Prednisone 20 day taper given as 40mg PO QD for 5 days, 30mg PO QD for 5 days, 20mg PO QD for 5 days, 10mg PO QD for 5 days, then stop. Common side effects: Fluid retention, increased sweating, headache, insomnia, nervousness, mood swings, edema, muscle weakness, BP elevation, facial erythema, menstrual irregularities, hypokalemia, intraocular pressure increase, shortness of breath, weight gain.

5. Nasal saline ad lib

g. If an Investigational Device (ID) is involved, provide the following information: (1) name of device, (2) manufacturer, (3) status with Food and Drug Administration and ID#, (4) review of animal studies and previous human studies, (5) reported adverse effects. – Not applicable

## 9. DATA COLLECTION

*As above. The data which will be collected is clinic nasal endoscopy score, visual analogue score (VAS), SNOT 20 score and initial CT of paranasal sinuses with Lund7*

*McKay score. Response to treatment as recorded by subjective scoring systems above will be recorded in hard copy and be kept by PI in secure, locked drawer.*

#### 10. LABELING & STORAGE OF DATA & SPECIMENS

*Description of consent document storage/time/destroyed/disposed, research records and data storage/time/destroyed/disposed, hard copies vs. electronic, research specimens storage/time/destroyed/disposed and any special storage conditions*

#### 11. DATA ANALYSIS

*Data will be compiled and statistical analysis will be made using PRISM software*

